Study Protocol – Version 5, March 30, 2023

NCT05503823

Project Title: Investigating Transcranial Alternating Current Stimulation (tACS) Preconditioning Effects on Resting and Active Motor Threshold

1. Summary of the Project

Transcranial Magnetic Stimulation (TMS) is a non-invasive brain stimulation technique which uses a large and rapidly changing magnetic field pulse for stimulation. Exposure to TMS has been associated with the improvement of the brain's plasticity and memory loss [1]. These after-effects of TMS are temporal and short-term. However, repetitive sessions of preconditioning the brain before TMS has the potential to extend the duration of these after-effects while also reducing the amount of exposure necessary for observable results. The proposed study focuses on providing some insight on the effects of priming the brain via Transcranial Alternating Current Stimulation (tACS) and Transcranial Random Noise Stimulation (tRNS) before applying TMS.

In this study, single pulse TMS is applied over the primary motor cortex, specifically for the hand area to find the resting and active motor thresholds. The Resting Motor Threshold (RMT) is the lowest intensity to produce involuntary hand twitches while the hand is at a relaxed position or when the motor evoked potential has a peak-to-peak amplitude of greater than $50\mu\text{V}$ for 5 of 10 trials [2][3]. The active motor threshold (AMT) is similarly the lowest intensity at which the participant shows involuntary hand twitches, but this time while the hand is contracted. AMT is also measured similarly as the lowest intensity at which the motor evoked potential has a peak-to-peak amplitude of greater than $100\mu\text{V}$ for 5 of 10 trials [4][5]. The electromyography (EMG) of the First Dorsal Interosseous muscle (FDI) is recorded before the application of tACS as a baseline for both RMT and AMT. Then the tACS/tRNS is applied at 40Hz for 10 minutes with the active electrode over the exact location of the TMS application (the hand area of the primary motor cortex) and the reference over the right supraorbital area. Then the EMG is recorded immediately after tACS/tRNS, 30 minutes after, and 1 hour after exposure to tACS/tRNS. These recordings are done both in resting and active states of the muscle. The objective is to observe a change in the motor evoked potentials (MEPs) after exposure to tACS or tRNS and analyze the time of the sustained MEP change.

The proposed study will be tested on 50 cognitively healthy participants from a diverse age group (18-95).

An increase in the peak-to-peak value of MEP post-tACS or post-tRNS could prove to indicate as a new technique to lower the RMT, resulting in lower intensity exposure to TMS. This will be helpful when TMS is used for treatments such as depression disorders. The goal of this study is to eventually find a preconditioning technique to increase the duration of TMS sessions to help in treatment of initial stages of Alzheimer's disease.

2. Background

Previous studies have investigated preconditioning the brain through electrical stimulation of the brain mainly using direct current application [6][7]. These studies show promising improvement of the motor evoked potential (MEP) when transcranial electric stimulation (tES)

techniques such as tDCS (transcranial direct current stimulation) are applied before a session of TMS [6][7]. This study attempts to extend the previous findings by investigating the effects of alternating current and random noise stimulations on the brain known as tACS and tRNS respectively.

tDCS

tDCS is electrical stimulation of the brain using direct current. The study by Lang et al [6] shows a prominent increase of motor evoked potential peak-to-peak amplitude caused by TMS after stimulation of the brain with tDCS over the motor cortex. This study concludes that preconditioning the brain with tDCS effectively improves the cortical plasticity during rapid TMS while also controlling the direction of TMS induced after-effects by changing the placement of the cathode and anode during application of electrical stimulation [6].

A second study conducted by Cosentino et al [7] also investigates the effects of priming the brain using tDCS in a similar setting as the previous study. Contrary to the previous study, this study shows that neither cathodal nor anodal stimulation caused a higher MEP than the baseline [7].

tACS

tACS is electrical stimulation of the brain using alternating current. This stimulation is bipolar therefore, it is not expected to see any difference between the cathodal and anodal after-effects of the priming. In this study we will extend the previous studies to investigate the effects of pre-conditioning the brain using tACS.

tRNS

tRNS is electrical stimulation of the brain using random noise. This stimulation is also bipolar therefore, it is not expected to see any difference between the cathodal and anodal after-effects of the priming. In the second part of this study, we will investigate the effects of pre-conditioning the brain using tRNS.

3. Research Instruments

The following instruments are used for the research:

- 1) Position sensor
- 2) Transcranial Magnetic Stimulation (TMS)
- 3) Electromyography (EMG)
- 4) Transcranial altering current stimulation (tACS)
- 5) Transcranial random noise stimulation (tRNS)
- 6) Sphygmomanometer
- 7) Oximeter
- 8) Two questionnaires:
 - a. Montreal Cognitive Assessment (MoCA) for screening the participants of no cognitive impairment.

b. Questionnaire to exclude any participant using the exclusion criteria and gather information about possible confounding variables. This will be provided upon both visits.

Both questionnaires are attached to this document.

Position Sensor Camera

Vicra position sensor camera will be used to record the exact position, direction, and tilt of the TMS coil during each pulse. This is done by carefully determining facial landmarks and measuring the participant's scalp using a headband and a pointer equipped with position sensors. While the headband is around the participant's head, the RA will use the pointer to identify the nasion, notch above the tragus of the left and right ear, forehead, top of the head, back of the head, and the left and right sides of the head. The Brainsight software uses these positions marked by the pointer to track the position of all the stimulation pulses to accurately stimulate the exact same position for each RMT and AMT recording.

Transcranial Magnetic Stimulation (TMS)

TMS will be applied on each participant to measure RMT:

- 1) Before tACS/tRNS
- 2) Immediately after tACS/tRNS
- 3) 30 minutes after tACS/tRNS
- 4) 1 hour after tACS/tRNS

The following parameters will be applied for all eight applications of the TMS:

| PARAMETER | DESCRIPTION/VALUE |
|----------------------|---|
| DEVICE | Magstim Rapid2 Stimulator on single TMS pulse setting with the figure-of-eight AirFilm Coil |
| APPLICATION LOCATION | On C3 over the hand area of primary motor cortex |

Electromyography (EMG)

EMG will be recorded during all TMS sessions using the following parameters:

| PARAMETER | DESCRIPTION/VALUE |
|-------------------------|---|
| DEVICE | EMG Recording Pod, Brainsight 2 |
| APPLICATION LOCATION | Two electrodes on First Dorsal Interosseous (FDI) muscle and the reference electrode on top of the wrist (head of ulna) |
| SAMPLING FREQUENCY | 3 kHz |
| DURATION FOR EACH PULSE | 50 ms before the pulse, 200 ms after the pulse |

Transcranial altering current stimulation (tACS)

The following parameters will be applied during the tACS sessions:

| PARAMETER | DESCRIPTION/VALUE |
|----------------------|---|
| DEVICE | tES, Soterix Medical Inc. (Model: 2001) |
| FREQUENCY | 40 Hz |
| APPLICATION LOCATION | Active electrode on C3 over the right-hand area of the motor cortex and reference on the contralateral motor cortex |
| INTENSITY | 0.75 mA (1.5 mA peak-to-peak) |
| Waveform | Sinusoidal (bipolar) |
| DURATION | 10 minutes |

Transcranial random noise stimulation (tRNS)

The following parameters will be applied during the tRNS sessions:

| PARAMETER | DESCRIPTION/VALUE |
|----------------------|---|
| DEVICE | tES, Soterix Medical Inc. (Model: 2001) |
| APPLICATION LOCATION | Active electrode on C3 over the right-hand area of the motor cortex and reference on the contralateral motor cortex |
| INTENSITY | 0.75 mA (1.5 mA peak-to-peak) |
| Waveform | Random Noise (bipolar) |
| DURATION | 10 minutes |

4. Participants

This research requires a total of 50 healthy participants who must meet the following inclusion criteria:

- Between the ages of 18 years and 95 years
- MoCA score ≥ 26
- Not diagnosed with any restricting conditions such as history of seizures, epilepsy, having pacemakers, being pregnant, having a diagnosed major psychotic disorder, having pain relief medication on a daily basis, or having any metallic implants that might cause a conflict while using TMS.
- Not being on any regular nervous system medication for depression, anxiety, sleep, etc.
- Not have had any brain injury

All participants will be assessed by MoCA and will fill out the questionnaire after signing the consent form.

5. Recruitment

Potential participants will be recruited by providing a poster on the supervisor's webpage <https://home.cc.umanitoba.ca/~[name]/> and Biomedical Engineering webpage of University of Manitoba at <https://umanitoba.ca/engineering/biomedical-engineering>. Furthermore, posters will be placed around the University of Manitoba campus with permission to recruit

participants. The posters will have information about the project and an email to contact the team to participate in the study.

6. Data Analysis

Motor Evoked Potential (MEP)

Motor evoked potential, as shown in Figure 1, is the involuntary response of the muscle due to the magnetic stimulation to the corresponding area of the brain, hand area for the primary motor cortex. In this study, we are collecting the FDI (first dorsal interosseous) EMG to observe the change in the peak-to-peak value of the MEP. A noticeable increase in the peak-to-peak value of the MEP, while a constant amount of TMS intensity is applied to the brain before and after priming via tACS/tRNS is used, suggests that the priming has been in fact successful, and the motor threshold has been reduced due to the priming.

The EMG recorded before and after tACS/tRNS will be compared to observe any change in the MEP.

[figure not shown]

Figure 1. Active FDI EMG with MEP and cSP

Cortical Silent Period (cSP)

Cortical silent period (cSP) refers to the silent period that is followed immediately after MEP. This period is only observable in an active muscle EMG. By measuring the duration of cSP we can estimate the intracortical inhibition of pyramidal neurons caused by activation of GABA_B (gamma-aminobutyric acids) [8]. A noticeable decrease in the cSP potentially indicates that the preconditioning stimulation via tACS/tRNS has been effective. In this study we will be collecting the active muscle EMG during TMS sessions before and after application of tACS/tRNS.

7. Informed Consent

A consent form will be provided to the volunteers at the beginning of the two-hour session to inform them about the requirements of the study, risks and benefits, withdrawal process, confidentiality policies, and debriefing procedure. The volunteers who wish to participate in the

study will sign the consent form and will be provided with a copy of the form for safekeeping. The original form will be locked along with the participants assigned code in a locked cabinet in the research supervisor's office.

8. Procedure

All volunteers will be contacted by the research assistant (RA) via phone or email. The RA will briefly explain the study while also setting a time slot for the volunteers to come in and read the consent form and discuss it. If the participant wishes to continue the study and signs the consent form, the RA can start the initial assessments by taking the MoCA test and having the participant fill out the questionnaire. Once the volunteers meet the criteria of the study, they will be assigned a code and enrolled to the study and all their data will be recorded under the assigned code. The consent forms which contain the participants code and contact information will be locked in a cabinet in the PI's office.

Once enrolled, participants will be examined to achieve their RMT (resting motor threshold). To do this, first the Vicra camera is turned on and the scalp of the participant is measured and saved on the computer. Then single TMS pulses are applied with the coil positioned over the right-hand area of the primary motor cortex on the left hemisphere (C3) with initial intensity of 50% of the maximum intensity. The coil position will be adjusted over the primary motor cortex until the "hotspot" is found and an involuntary right-thumb twitch is observed. If no twitch was observed after few pulses, the intensity will be increased by increments of 5% until the hotspot is found. Once the "hotspot" is found, it will be marked as a target using the coordinating camera and the intensity will be reduced by decrements of 1% to the minimum intensity where a twitch is observed. The coordinating camera will be used to record the exact position and direction of the coil while a hotspot was achieved to help us accurately stimulate the hotspot once it is found. Similar procedure is applied to determine RMT for the right side of the brain, i.e. left hand movement.

Once the minimum intensity is recorded for the RMT, the participant gets a 10-minute break from the stimulation. During this time, the RA will measure the blood pressure and oxygen level and connect the electrodes over the FDI muscle of the right hand to record EMG and prepare the participant for the TMS session. During the first TMS session, 10 single pulses are applied to the participant over the hotspot recorded by the coordinating camera. The resting EMG of the corresponding muscle in a relaxed position will be recorded for further investigation under the participant code name. Immediately after, the participant will be asked to gently hold the arm rest of the chair and the active EMG will be recorded over 10 single pulses of TMS.

The participant will be given a 5-minute break, during which the RA place the tACS active electrode on the hotspot marked by the coordinating camera and the reference on the contralateral motor cortex. When the electrodes are all set up, tACS will be applied gradually from lower current intensity to higher for 1 minute to allow the participant to adjust to the current. The current is applied at 40 Hz frequency for the duration of 10 minutes. Immediately after the application of tACS the participant's resting and active EMG will be recorded similar to the pre-tACS procedure, with 10 pulses of TMS for each of the resting and active experiments.

Also, the blood pressure and oxygen level will be remeasured. A similar procedure will be followed to record the resting and active EMG after 30 minutes and after 1 hour from the initial application of tACS.

During the second session, the participant will be monitored by the exclusion questionnaire. If the participant passes the criteria, the RMT will be measured again and a similar procedure to the first session will be followed while tRNS is used instead of tACS. The second session can begin after 4 hours following the first session and may occur on a separate day depending on the participant's availability.

Each of these procedures will be applied once on each participant and the experiment for each participant will be done after one or two visits to the laboratory.

Data collection for the study will take place for a period of one year.

All the data will be deleted and destroyed 3 years after completion of the study.

9. Deception

There is no deception in this study.

10. Feedback/Debriefing

Participants can ask about their own performance and result of the study once the study is completed and published.

11. Risks and Benefits

Exposing the brain to magnetic energy via TMS might have some mild risks such as tingling in the jaw and the arm and mild headaches. However, participants who are pregnant, use pacemakers, or have any metallic implants (e.g., dental implants) will be excluded from the study to avoid any conflict while exposed to magnetic energy.

There are also some potential mild risks while preconditioning the brain using tACS/tRNS. These risks include mild pain, headaches, or fatigue. Participants may experience tingling, itching, burning sensation, or skin redness where electrodes are connected. Participants that have history of seizure or epilepsy will be excluded from the study as tACS and tRNS have limited information on the serious adverse effects.

There are no direct benefits concerning the participants from this study. However, the result of the study has the potential to provide sufficient means to treat early stages of memory loss for Alzheimer Dementia (AD) patients.

12. Anonymizing/Confidentiality

All participants' personal information, including their name and contact number will be remained confidential. Each participant will be assigned with a de-identified code and the master file containing the names and codes will be saved on a secure server, ECE server. The assessment data will be saved on the PI's BME server which is physically separate from the ECE server.

13. Compensation

This study does not provide any compensation for the participants.

14. Dissemination

The study result will be presented in relevant seminars, conferences, and journal paper publications.

15. References

- [1] S. J. Boniface, U. Ziemann, *Plasticity in the Human Nervous System: Investigations with Transcranial Magnetic Stimulation*. Cambridge, University of Cambridge Press, UK, 2003, Ch. 1-2, pp. 1-61. [Online]. Available: <https://web-p.ebscohost.com.umi.idm.oclc.org/ehost/detail/detail?vid=0&sid=c2c48531-d39d-4217-b80f-ff0b8b8d2840%40redis&bdata=JnNpdGU9ZWhvc3QtbGl2ZQ%3d%3d#AN=120392&db=e000xna>. [Accessed: June 20, 2022]

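### The EMG record ends 200 ms after each pulse, so long silent periods would be right-censored and a true fall in cSP might be understated

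*Combined protocol and SAP*

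**What the plan says.** Section 3 (Electromyography) introduces its settings with "EMG will be recorded during all TMS sessions using the following parameters". The table then gives a per-pulse duration of "50 ms before the pulse, 200 ms after the pulse" and a 3 kHz sampling rate. No separate setting is given for active-muscle recordings.

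Section 6 (Cortical Silent Period) places the silent period directly after the MEP: "Cortical silent period (cSP) refers to the silent period that is followed immediately after MEP". Duration is the quantity of interest: "By measuring the duration of cSP we can estimate the intracortical inhibition of pyramidal neurons". The expected direction is also stated: "A noticeable decrease in the cSP potentially indicates that the preconditioning stimulation via tACS/tRNS has been effective".

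Section 8 provides the data. At each time point "the active EMG will be recorded over 10 single pulses of TMS". The only rule for stimulation intensity concerns the resting threshold, where "the intensity will be reduced by decrements of 1% to the minimum intensity where a twitch is observed". No higher intensity is stated for the active recordings.

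The readable text gives no expected cSP duration or spread, no reason for choosing 200 ms, and no rule for a trace that is still silent when the record stops.

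**The concern.** A duration needs an observed end. The cSP ends when voluntary EMG returns, and that can be seen only if it happens inside the record. Beyond 200 ms the analyst knows only that the silence lasted at least that long.

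This censoring would not fall evenly on the two sides of the comparison. If tACS or tRNS shortens the cSP, the pre-stimulation values are the longer ones and reach the limit more often. Scoring unfinished traces at 200 ms, or leaving them out, would lower the baseline mean more than the post-stimulation mean. The measured decrease would then be too small, which is a bias against the direction that Section 6 looks for. If stimulation lengthened the cSP, the limit would hide part of that as well.

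EMG that was never recorded cannot be recovered at the analysis stage, so the point has to be settled before data collection.

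**Working it through.** The plan states no cSP figure, so there is nothing to reproduce. The check asks how much of a true decrease survives a 200 ms limit under stated assumptions.

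**From the documents:** the record ends at 200 ms after the pulse, and there are 10 active pulses per time point.

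**Assumed:** the time from pulse to end of silence is normal at baseline with mean μ of 100 to 180 ms and SD s of 30 to 40 ms (total spread over pulses and participants). The true decrease is 15 ms. Post value = baseline − 15 + noise with SD 10, so the post SD is √(s² + 10²).

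**Formulas**, with limit c and a = (c − μ)/s:
- share censored = 1 − Φ(a)
- mean if unfinished traces are scored at c: μΦ(a) − sφ(a) + c(1 − Φ(a))
- mean if unfinished traces are dropped: μ − sφ(a)/Φ(a)

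**Worked case, μ = 180, s = 40, c = 200**
- Baseline: a = 20/40 = 0.5, Φ = 0.6915, φ = 0.3521. Censored: 30.9%. Mean = 124.46 − 14.08 + 61.71 = 172.09 ms.
- Post: mean 165, SD √1700 = 41.23, a = 35/41.23 = 0.849, Φ = 0.8020, φ = 0.2783. Censored: 19.8%. Mean = 132.33 − 11.47 + 39.60 = 160.46 ms.
- Measured decrease: 172.09 − 160.46 = 11.6 ms, or 78% of the true 15 ms.
- If unfinished traces are dropped: 159.63 − 150.69 = 8.9 ms.

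**Range at c = 200 ms, unfinished traces scored at the limit**

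| Mean (ms) | SD (ms) | Baseline censored | Measured decrease (true 15 ms) |
|---|---|---|---|
| 100 | 30 | 0.04% | 15.0 |
| 100 | 40 | 0.6% | 14.9 |
| 120 | 40 | 2.3% | 14.8 |
| 150 | 30 | 4.8% | 14.6 |
| 150 | 40 | 10.6% | 14.0 |
| 180 | 30 | 25.2% | 12.6 |
| 180 | 40 | 30.9% | 11.6 |

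**A lengthening.** For the same worked case with a true 15 ms increase, the post mean is 195, a = 5/41.23 = 0.121, and the limited mean is 106.91 − 16.33 + 90.35 = 180.93 ms. The measured increase is 180.93 − 172.09 = 8.8 ms.

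**Scale of measurement.** The table counts time from the pulse. The cSP starts only after the MEP, so on the duration scale the limit is lower. If the MEP ends at an assumed 20 to 50 ms, the longest measurable cSP is 180 to 150 ms. With a duration limit of 170 ms, assumed mean cSP of 80 to 100 ms and SD of 20 to 40 ms (same SD before and after), at most 4.0% of baseline traces are censored and 97 to 100% of the decrease is kept. The pattern is the same: almost nothing is lost for short silent periods, and more as the mean nears the limit.

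**The case against.** The strongest reply is that nothing in the documents shows the limit to bind. No stated value places the cSP near 200 ms, and the only intensity rule is a twitch threshold. Figure 1 is described as an active recording showing both MEP and cSP, but it is missing from the copy reviewed, and it may show EMG returning well inside the window. A cited study of cSP duration might also bear on the point and was not available. All of this stands, and it is why the point is conditional.

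Four stronger readings are tempting and are not supported:

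- **That the window does shrink the decrease.** With mean ends of silence of 100 to 120 ms, at least 14.8 of the 15 ms is kept.
- **That about 40% of the effect is lost.** That figure (9.1 of 15 ms) needs a mean of 180 ms together with an assumed usable limit of 180 ms. The mean then sits on the limit, so half the baseline traces are censored by construction.
- **That participants with long silent periods drop out.** There are 10 active pulses per time point, and a participant is lost there only if every usable pulse is unfinished. The plan does not propose dropping pulses in any case.
- **That the trial's main objective is damaged.** Section 1 states the objective as a change in the MEP and how long it lasts. The cSP is a second measure, and Section 6 says only that a decrease potentially points to an effect. The window does not limit the reading of MEP amplitude.

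**Conclusion.** The point holds in conditional form and is minor. The 200 ms record applies to the recordings that yield the cSP, any silence outlasting it is right-censored, and that censoring would pull a true decrease toward zero.

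Under the stated assumptions, a 15 ms decrease would be measured as anything from 15.0 ms (negligible loss) to about 11.6 ms (a loss of 3.4/15, or 23%) when unfinished traces are scored at 200 ms. The loss is larger if they are dropped. Which end of the range applies depends wholly on a cSP distribution that the readable text does not give. The case for acting is that the change is small and the missing data could not be recovered later.

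**What to change.** **Section 3, EMG table.** Lengthen the post-pulse record for active-state pulses, for example to 500 ms if the device allows. Keep the same setting at all four time points and in both sessions.

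**Section 6, cSP.** State the criterion for EMG return. Treat any pulse without return inside the window as right-censored; do not drop it or score it at the window end. Report the number of such pulses by time point and by session. One workable analysis is a mixed model for right-censored durations with a participant effect. A simpler one is each participant's median over the 10 pulses, which is still observed when up to four of them are censored at the window end.

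If the device cannot record longer, the censoring rule and the counts alone would show readers whether the limit mattered.

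**Cost.** No extra pulses, visits or staff. At 3 kHz the record grows from 250 ms × 3 = 750 samples to 550 ms × 3 = 1,650 samples per active pulse. The censored analysis adds a little work. The documents do not say whether the record length can be changed on this device, so that should be confirmed first.

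### Section 6 reads an undefined before-after rise in MEP as successful priming and a lower motor threshold, with no primary contrast and no no-current comparison

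*Combined protocol and SAP*

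**What the plan says.** Section 6 (Data Analysis) is the whole analysis plan. The comparison is given in one sentence: "The EMG recorded before and after tACS/tRNS will be compared to observe any change in the MEP". The trigger in the rule for reading it is "A noticeable increase in the peak-to-peak value of the MEP". The condition attached to that rule is that the rise occurs "while a constant amount of TMS intensity is applied to the brain before and after priming". Such a rise, the section says, "suggests that the priming has been in fact successful, and the motor threshold has been reduced due to the priming". For the cortical silent period the rule is similar: "A noticeable decrease in the cSP potentially indicates that the preconditioning stimulation via tACS/tRNS has been effective". Section 1 makes the same link to threshold, saying that a post-stimulation MEP rise "could prove to indicate as a new technique to lower the RMT", and the project title names "Preconditioning Effects on Resting and Active Motor Threshold" as the subject.

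Other sections supply the design:

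- **Section 1** sets a baseline and three later recordings (immediately, 30 minutes, 1 hour), each at rest and in contraction. Its objective covers both a change in MEP and how long the change lasts. It defines RMT as a lowest intensity, judged either by visible twitch or by an MEP above 50 µV in 5 of 10 trials.
- **Section 3** lists TMS for measuring RMT at all four times, and says that coil position, direction and tilt are tracked at each pulse.
- **Section 8** gives tACS in the first session and tRNS in the second, which may start 4 hours later. Each recording after stimulation consists of 10 resting and 10 active pulses.

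**The concern.** Two inferences in Section 6 go further than the design allows.

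The first is attribution. Both sessions deliver current, in the same order for everyone, and no sham, no-current or time-only session is described. A change from baseline therefore mixes any effect of current with the passage of time, arousal and the repeated pulses themselves. tRNS cannot act as the control for tACS, because it is itself active and always second. With no size, test or primary contrast fixed in advance, a chance result among many comparisons could also be reported as priming.

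The second is the step from MEP size to threshold. The outcome in the title is a threshold, and Section 1 defines that as a lowest intensity. Section 6 infers a lower threshold from a larger response at one fixed intensity.

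At stake is the study's main conclusion: the text as written permits a report that the stimulation lowered the motor threshold when the data may show only a larger MEP later in the session.

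**Working it through.** **Plan's own figures.** The only design figure is 50 participants (Section 4). No alpha, power, effect size or SD accompanies it, so there is nothing to reproduce. Everything below is illustration on assumed values.

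**Step 1: comparisons left open.** 2 stimulations × 3 post times × 3 outcomes (resting MEP, active MEP, cSP) = 18. Thresholds are not counted.

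**Step 2: chance.** Assume each comparison is tested at two-sided 5%, so that a false result in the favourable direction has probability 0.025.

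- Independent: 1 − 0.975^18 = 0.366, or 37%.
- Common correlation 0.3, 0.5, 0.7 (equicorrelated normal): 26%, 20%, 14%.
- Correlation 0.5 among the three times sharing a baseline, and 0 or 0.25 between families: 32% or 26%.

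The range is therefore about 14% to 37%.

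**Step 3: drift.** Assume that current has no effect, that MEP drifts up by 20% over the session, and that n = 50. The log-ratio SD is not in the documents, so 0.4 to 0.8 is assumed. For a paired t-test the non-centrality is δ = ln(1.2) × √50 / SD, and the two-sided 5% critical value on 49 df is 2.010.

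| Log-ratio SD | δ | Significant rise, one contrast at 5% | At 2.5% | At least one rise under Holm, both sessions drifting (independent) |
|---|---|---|---|---|
| 0.4 | 3.22 | 88% | 82% | 97% |
| 0.6 | 2.15 | 56% | 44% | 69% |
| 0.8 | 1.61 | 35% | 25% | 44% |

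The last column is 1 − (1 − p)², with p from the column before it. A 10% drift gives 38% down to 13% for one contrast at 5%. A formal test therefore limits chance findings but does nothing about drift. A downward drift would hide a real rise instead.

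**Step 4: threshold, by comparing sections.**

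- Section 1: threshold is a lowest intensity, by twitch or by the 50 µV criterion.
- Section 8: RMT is found at baseline by twitch, lowering intensity in 1% steps, and the EMG electrodes go on afterwards. RMT is found again at the start of the second session.
- Section 3: TMS is applied to measure RMT before, immediately after, 30 minutes after and 1 hour after stimulation.
- Section 8: the recordings after stimulation are described only as 10-pulse blocks, done in a similar way to the pre-tACS procedure.
- Section 6: a lower threshold is inferred from MEP size at constant intensity.

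Sections 3 and 8 thus differ on whether threshold is re-measured after stimulation. If it is not, the Section 6 inference is the only route to the title outcome, and a response at one intensity does not locate the lowest effective intensity.

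**The case against.** The text is hedged. It says that a rise suggests, or potentially indicates, an effect. Section 1 aims at insight and at observing a change, and no confirmatory hypothesis or significance claim is made. Each participant has a baseline in the same session, TMS intensity is to be held constant, and the coil is tracked. All of this stands and lowers the severity. It does not remove the problem: these controls limit some variation but not effects of time, arousal or repeated pulses, and the hedged sentence is still the only rule for drawing a conclusion.

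The alpha, SDs, correlations and drift sizes are assumed, and the chance figure moves widely with them. That also stands. The figures show vulnerability and do not measure an error in this study.

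Three stronger readings are tempting and are not supported:

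- **That threshold is never re-measured after stimulation.** Section 3 says it is measured at all four times, and the brief account in Section 8 does not exclude it. The sections conflict; neither settles the matter.
- **That a larger MEP can be shown to leave threshold unchanged.** Suppose five pulses rise from 100 to 200 µV while five stay at 40 µV. The mean goes from 70 to 120 µV, with 5 of 10 above 50 µV both times. This shows only that a larger mean is not proof. At a lower intensity the enlarged responses might still pass, and the baseline procedure in Section 8 uses the twitch criterion anyway.
- **That one particular test is required.** The choice of muscle state, time, summary and test is open, provided it is fixed before analysis.

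**Conclusion.** The point holds, as one to fix before analysis. Section 6 allows an unspecified before-after rise to be read as an effect of priming and as a lower threshold, and the design supports neither step on its own. The missing primary contrast leaves about 18 comparisons open, with a 14% to 37% chance of at least one false favourable result if each were tested at two-sided 5%. An assumed 20% drift would pass a single 5% test in 35% to 88% of trials of 50, for log-ratio SDs of 0.8 to 0.4. The attribution and threshold problems do not depend on those numbers.

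A reader might infer that the plan asserts causation outright, or that any observed rise would be spurious. The documents support neither: the language is tentative, and a real effect is possible. The fault is that this design could not tell it from drift.

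**What to change.** 1. **Reword Section 6.** For example: *A within-session change in MEP or cSP is reported as an uncontrolled before-after change and is not attributed to tACS or tRNS. Any difference between tACS and tRNS is confounded with session order. A change in MEP size at constant TMS intensity is not reported as a change in motor threshold.*
2. **Replace the undefined criterion** with one pre-specified primary contrast per stimulation, with an interval and control of error across the two. One workable choice is each participant's mean log resting MEP, immediately after minus baseline, by two-sided paired t-test with Holm across tACS and tRNS (smaller p below 0.025, then the other below 0.05). Report 97.5% intervals, and state that Holm governs the declaration, since an effect declared at the second step can have a 97.5% interval that includes no change. Another state, time or summary is acceptable if fixed before analysis. This limits chance findings only; drift is dealt with by item 1.
3. **Report as secondary, with intervals,** active MEP, cSP, any re-measured RMT or AMT, and the 30-minute and 1-hour times, which the stated aim on duration needs. Reconcile Sections 3 and 8 on whether RMT and AMT are measured after stimulation.

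**Cost.** Analysis time and a more modest claim; no change to visits, participants or recordings. For the example contrast at n = 50, the 97.5% half-width on the log scale is 2.312 × SD / √50, so an interval centred on no change runs from 0.88 to 1.14 (SD 0.4) or 0.77 to 1.30 (SD 0.8). For 80% power at the first Holm step the log-mean ratio must be about 1.20 (SD 0.4) to 1.43 (SD 0.8), a rise of 20% to 43%. If 20% of pulses are non-responses that do not change, the evoked rise must be larger: 1.196^(1/0.8) = 1.25 and 1.4305^(1/0.8) = 1.56, about 25% to 56%. Smaller changes would often not be declared. A causal claim would need a no-current comparison, a design change for the sponsor to weigh that lies outside this fix.
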